5.2 Study Plan and Procedures

Study RBUS with UJA will be obtained within 10 days following CT diagnosis of ureteral calculus. Ureteral jet data will be documented and patients will be followed prospectively for 42 days at 2 weeks, 4 weeks and 42 days (6 weeks) after diagnostic CT. Specifically, patients will be followed for spontaneous stone passage and will be expected to record date of stone retrieval. If specific date of stone passage is not known, date of standard of care imaging confirming absence of stone(s) will be used as the date of stone passage. If spontaneous stone passage is not achieved, patients will be counseled regarding further standard of care treatment options including surgical stone removal. If surgical intervention is indicated, time to surgical procedure will also be recorded. This patient cohort will be analyzed retrospectively to determine whether RBUS with UJA is predictive of spontaneous stone passage versus need for surgical intervention over a 42-day period.

Interpretation of RBUS and UJA:

Abdominal radiologists will interpret the RBUS research reads. All grey scale and color Doppler examinations will be performed by means of a commercially available unit with a 1-5 MHz phased array transducer or a 1-6 curved transducer. Flow toward the transducer is assigned a red color on Doppler. For grey scale evaluation, the presence or absence of urinary tract stones, size (longest axis in mm) and location- R, L, upper pole, interpolar and lower pole of the kidneys, proximal ureter, distal ureter and bladder- will be documented. The level of the renal pelvis represents the interpolar kidney with upper and lower pole above and below this level. For this study, a urinary tract stone will be termed an echogenic focus that demonstrates either posterior acoustic shadowing and or twinkle artifact on color Doppler images. In addition, presence of hydronephrosis (mild, moderate, and severe) will be documented. For the purpose of this read, hydronephrosis will be defined as such: mild hydronephrosis - urine fills the intra and extra renal pelvis and the major calyces are dilated; moderate hydronephrosis – above + dilatation of the minor calyx with preservation of the renal parenchyma; severe hydronephrosis – above +

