5.3 Study Follow-up

After study RBUS is obtained, patients will be followed prospectively by telephone call at 2 weeks, 4 weeks and 42 days (6 weeks) from the time of diagnostic CT. They will be followed for spontaneous stone passage, and be asked to keep record of when this occurs. During the 42-day follow up, their course will also be monitored for ED visits, surgical intervention and hospital admissions. All currently available medical records such as Clindesk, Allscripts, Compass, HMED will be reviewed retrospectively to follow participants' clinical course, specifically to determine the need for surgical intervention or spontaneous stone passage. Billing records may also be used to identify patients who underwent surgical intervention based on CPT codes. Evaluation of the patient's emergency room records with a focus on their presenting symptomatology and initial evaluation by the emergency provider will be performed. Any additional laboratory tests and/or imaging obtained during their emergency room or office visit will also be reviewed and collected for study purposes.

Surgical intervention, including ureteral stent or nephrostomy tube placement, ureteroscopy/laser lithotripsy, or extracorporeal shockwave lithotripsy (ESWL) will be instituted, as per standard of care. A follow up telephone call at 2 weeks, 4 weeks and 42

days (6 weeks) from the time of diagnostic CT will be performed in case of care received outside of the Barnes-Jewish Hospital (BJH) system and medical records reviewed for ER visits, hospital admissions and surgical intervention.

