7.0 STATISTICAL CONSIDERATIONS

7.1 Study Objectives and Endpoints

Primary Outcome:

To determine if RBUS with UJA is prognostic of stone passage versus need for

surgical intervention:

1. Passage of stone as assessed by patient self-report and/or collection of stone or imaging.
2. Need for further medical attention as collected by chart review and phone interview for ED visit, hospitalization, or need for surgical intervention during the 42-day follow-up period.

Secondary Outcomes:

1. To determine if RBUS with UJA, in conjunction with standard of care laboratory data and history and physical confers non-inferior information compared to non-contrasted CT:
 - a. Urologist will review the patient's de-identified/coded history and physical, laboratory studies, and RBUS with UJA and make an assessment and treatment recommendations. The urologist will be blinded to the results of the CT. Comparison will be made between the CT diagnosis and the blinded assessment of the urologist.
2. To determine if the natural history and rate and time of stone passage for ureteral stones of differing locations (proximal, mid or distal ureter) and sizes (<2mm, 2-4mm, 5mm, 6-7mm, 9-10mm):
 - a. Assessment of the stone location and size to be conducted by a radiologist.

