7.3 Data Analysis

Primary objective:

This patient cohort will be analyzed retrospectively to determine whether US with UJA is predictive of spontaneous stone passage versus need for surgical intervention. Kaplan-Meier curve will be used to test time to spontaneous stone passage between the two groups. A chi-square test of independence will be used to test intervention rates between the two groups. A multivariate analysis will also be conducted controlling for such variables as age, gender, BMI, side, size of stone, and stone passage. A Cox-proportional hazards model will be used for time to spontaneous stone passage and logistic regression will be used for intervention.

Due to the unforeseen difficulty of recruitment and the uncertain assumptions of the initial power analysis, an interim statistical analysis is recommended to be performed when the recruitment reaches 50 patients. Based on the results, a decision will be made whether to continue recruitment to the initial 100 targeted patients, adjust the number of targeted patients based on a new power analysis, or to discontinue recruitment. The interim results

should not affect primary independent variables in the study as the radiologist performing the ultrasounds will not have access to the results.

Secondary objective 1:

Statistical analysis will be performed to determine diagnostic and treatment concordance between the two methods. A multivariate logistic regression model will also test patient factors that are associated with discordant results.

Secondary objective 2:

In a prospective manner, they will be followed to determine the natural history of ureteral stones with regard to stone passage. Average time to stone passage for each size category and stone location will be determined. Cox-proportional hazard models will be used to determine significant factors affecting time to stone passage.

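### Dating an undated passage to its clearing image makes that time late or at best exact, and can bias the hazard ratio if imaging timing or the undated share differs by group

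*Combined protocol and SAP*

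**What the plan says.** Section 5.2 puts the patient's own record first: patients "will be expected to record date of stone retrieval". The image date is a fallback, used only when the day of passage is unknown; then the "date of standard of care imaging confirming absence of stone(s) will be used as the date of stone passage".

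No follow-up image is fixed by the protocol. Appendix A lists CT and RBUS at baseline only, and section 5.5 leaves clinic visits to routine practice. Section 5.3 gathers later imaging as it happens: "Any additional laboratory tests and/or imaging obtained during their emergency room or office visit will also be reviewed and collected for study purposes". The same section has patients "followed prospectively by telephone call at 2 weeks, 4 weeks and 42 days (6 weeks) from the time of diagnostic CT", but the date rule makes no use of those calls.

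Section 7.1 lets passage be established in several ways: "Passage of stone as assessed by patient self-report and/or collection of stone or imaging".

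Section 7.3 uses the times in a Kaplan-Meier comparison and a Cox model for the primary objective. For secondary objective 2 it uses Cox models and a mean: "Average time to stone passage for each size category and stone location will be determined". It names no interval-censored or sensitivity analysis and states no censoring rule.

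**The concern.** An image without the stone shows only that passage happened before the image. Treating that day as the exact event day adds a one-sided error, whose size is set by when routine care happened to image the patient.

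Three things are at stake:

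- **Average time to passage** by size and location is inflated even if every group is imaged alike.
- **The jet-group comparison of passage times** can be biased. Nothing in the protocol makes imaging alike across jet groups or keeps treating clinicians unaware of the jet result. Patients with more symptoms or larger stones may well be imaged at different times.
- **The 42-day window** is left unclear. A patient may report an undated passage at the day-42 call and have the clearing image later. By self-report the passage falls inside the window; by the date rule it falls outside. The plan does not say which governs.

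**Working it through.** The plan gives no passage-time distribution, undated share or image timing, so there is no figure of its own to reproduce. Everything below rests on assumed inputs, except the 42-day window (sections 5.2 and 5.3) and the sample size of about 100 (section 7.2).

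**1. Mean time among true 42-day passers.** Assume exponential passage with median *m*. Then λ = ln 2 / *m*, F = 1 − exp(−42λ), and the mean among those passing by day 42 is 1/λ − 42(1 − F)/F.

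- *m* = 8: 11.54 − 42 × 0.0263/0.9737 = 10.4 days.
- *m* = 12: 17.31 − 42 × 0.0884/0.9116 = 13.2 days.

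Let a share *u* be undated, with the image uniform on days 28–42 (mean 35). The recorded mean is about the true mean + *u* × (35 − true mean).

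| Median | True mean | u = 5% | 10% | 20% | 40% |
|---|---|---|---|---|---|
| 8 | 10.4 | 11.6 | 12.9 | 15.3 | 20.2 |
| 12 | 13.2 | 14.3 | 15.4 | 17.6 | 21.9 |

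A simulation that dates a stone still present at its image to 7 days after passage gives nearly the same means for 20% and 40% undated: 15.4 and 20.4 (median 8), 17.7 and 22.2 (median 12).

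**2. Passages dated after day 42.** If the image is uniform on days 35–56, the part after day 42 is (56 − 42)/(56 − 35) = 2/3. The share of true 42-day passages dated late is then *u* × 2/3: 13% at 20% undated, 27% at 40%, and 3–7% at 5–10%.

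**3. Hazard ratio when the truth is 1.** The model is Cox to day 42 with two equal groups, a simplification because section 5.2 defines three jet groups. Ending at day 42 is a reading of the window, not a stated rule.

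- *Same timing and same undated share.* The recorded hazard ratio is 0.99–1.01, so no false effect arises. With images on days 28–56, rejection at N = 100 stays at about 5%.
- *Imaging near day 14 in one group and day 35 in the other.* With 20–40% undated the ratio is about 1.2–1.4 (median 12) or 1.3–1.6 (median 8; repeat runs put the top between 1.6 and 1.8). With 5–10% undated it is about 1.04–1.14, and at most 1.18 across repeats.
- *Same timing (days 28–56), but 50% undated in the weak-jet group and 20% in the other.* The ratio is 0.74 if 50% pass by day 42, and 0.66 if 80% do. The bias now makes weak-jet patients look slower. Earlier imaging of them makes them look faster, so the direction is not fixed.

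**4. Hazard ratio when the truth is 0.5.** With equal imaging on days 28–56 and 20–60% undated, the recorded ratio moves to 0.51–0.59. Power at N = 100 falls from 55–56% to 35–47% (50% passage) or from 80–81% to 42–66% (80% passage).

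**5. Interval censoring.** An exponential interval-censored likelihood was fitted to differential scenarios with true ratio 1. Undated passages were bounded by the last image with the stone (or the CT) and the first clear image. The ratio returned to 0.99–1.02, assuming that image timing carries no information about passage.

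**The case against.** The strongest reply is that the rule is only a fallback. Patients are asked to note the date and are called three times, so few passages may be undated. That stands: the documents do not give the share, and at 5–10% the shift in the mean is about 1–2.5 days. The assumed medians also imply that 91–97% pass by day 42 with no surgery modelled, so the figures show mechanism rather than forecast.

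A reader might infer more than the documents support:

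- *That image dates are the general rule.* They apply only when the date is unknown.
- *That the hazard ratio will be false.* This needs imaging timing or the undated share to differ by jet group or a linked factor. No passage says they differ, and none rules it out.
- *That a passage imaged after day 42 is recorded as no passage.* The plan states no such rule. Section 7.1 would let self-report count it, so the defect is that the case is unspecified.
- *That the whole of secondary objective 2, or the intervention analyses, fall with it.* That objective also covers the rate of passage, and the chi-square and logistic analyses of intervention do not use this date as their outcome.

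Interval censoring has limits too. A patient who missed a passage will tell a caller that none has occurred, so such a report cannot safely bound the time from below. The method also assumes non-informative image timing, which may fail if symptoms drive imaging.

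**Conclusion.** The point holds in a conditional form. For undated passages the rule gives times that are late or at best exact, and these enter the Kaplan-Meier, Cox and average-time analyses with no allowance for the uncertainty. Inflation of average time needs only that some passages are undated. A false hazard ratio needs a difference between groups and can run either way; without one, the harm is dilution and lost power. How to count a passage reported by day 42 but imaged later is an open gap.

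The size depends on the undated share and the image timing, neither of which the plan gives. It may be minor at 5–10% undated and is material at 20–40%. This should be changed, since the remedy is cheap, but it does not undermine the trial as a whole.

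**What to change.** Replace the image-date rule in section 5.2 and add matching text to section 7.3:

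1. Keep the patient-recorded date whenever it is known.
2. For an undated passage, take as lower bound the last image showing the stone, or the diagnostic CT if there is none later.
3. Take as upper bound the earlier of the first clear image and the first contact at which passage was reported. This also places an undated passage that was reported but never imaged.
4. Use the Turnbull estimator in place of Kaplan-Meier and an interval-censored proportional hazards model in place of Cox. Derive average times from the same analysis.
5. Use a telephone report of no passage as a lower bound only in a sensitivity analysis.
6. State that a passage reported by the day-42 call counts as within the window, and state the censoring rule.
7. Record how each passage was established, report the undated share and image timing by jet group, and repeat the analysis on confirmed passages.

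The cost is SAP wording, a few date and source fields, and a standard routine; no visit or procedure is added. Intervals will be somewhat wider, and the assumption of non-informative image timing should be stated and examined using the reports in item 7.

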1.2 Rationale

Due to the increasing use of CT and concern for radiation exposure, it is important to consider alternative diagnostic imaging modalities. We seek to evaluate patients who present to the Barnes-Jewish Hospital (BJH) ED and to the Urology office with renal colic who have been diagnosed with a ureteral stone. We seek to determine whether the findings on ureteral jet assessment (UJA) by RBUS are predictive of a patient's clinical outcome. Specifically, we seek to

evaluate whether the presence, absence or relative strength of the ipsilateral ureteral jet can predict spontaneous passage versus need for surgical intervention over a 42-day (6-week) time period. As many patients have a life-long affliction with nephrolithiasis[1], the potential for a considerable aggregate accumulation of radiation exposure over their lifespan can be excessive and should not be overlooked [5, 7, 8]. This patient population, especially those first diagnosed at a young age, would benefit from imaging modalities that do not involve radiation.

Evaluating the significance of UJA and RBUS in patients with renal colic will help define the role of this imaging modality, as an alternative to ionizing radiation-based studies. The prognosis of urolithiasis based on UJA will be defined, as well as the natural history of stones managed expectantly. We hypothesize that UJA showing weak or absent ureteral jet will predict obstruction and a higher rate of surgical treatment compared to spontaneous passage. We hypothesize that larger stones will be less likely to pass without surgical intervention.

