2.2 Secondary Objectives

1. To determine whether RBUS with UJA, in conjunction with standard of care history, physical examination and laboratory studies confers the same diagnostic information as the gold standard, non-contrast CT.
2. To determine the natural history and rate and time of stone passage for ureteral stones of differing locations (proximal, mid or distal ureter) and sizes (<2mm, 2-4mm, 5mm, 6-7mm, 9-10mm).

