3.0 PATIENT SELECTION

3.1 Inclusion Criteria

Patients must meet all of the following inclusion criteria to be eligible for study participation:

1. Age 18 and older at the time of consent
2. Willing and able to sign consent
3. CT diagnosis of ureteral stone with a stone burden less than or equal to 10mm

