5.0 STUDY PLAN

5.1 Screening and Informed Consent

Subjects will be seen and counseled by either the attending ED physician or their Urologist as part of the normal course of practice. Patients may be approached about study participation as soon as ureteral stone is suspected based on clinical presentation. Following CT diagnosis of ureteral stone, study team will further discuss study participation with the patient and complete the consent process if the patient is willing to participate.

The discussion regarding study participation will take place in a private setting, such as in a private consult room, to maintain confidentiality. HRPO approved consent form will be used to guide the consent process and document participant's consent. During the consent

process, the study team will explain RBUS with UJA, the normal anticipated course of a patient with the represented stone burden, potential risks and benefits of study participation, compensation and study follow-up schedule. Patients will be encouraged to ask questions and discuss the study with family. They will be given ample time to review the consent. It is possible that some participants may be contacted by phone to assess their interest in this study. If the participant expresses interest in the study, informed consent form will be mailed/e-mailed to him/her. This will be done in an effort to allow the patient ample time to read the consent at home, consider the study and discuss it with friends and family. This will not replace the face-to-face consent discussion the research team will have with the patient prior to signing the consent form.

Patients may decline to participate without an impact on their care. They will not be pressured to participate. No study related procedures will take place prior to the completion of the informed consent process and participant signing the HRPO approved consent.

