thin renal parenchyma. In addition, the presence or absence of hydroureter (proximal ureter, above the iliac bifurcation and distal ureter, below the iliac bifurcation) will be documented. If there is a stone in the renal pelvis, it will be recorded as interpolar kidney and noted as renal pelvis. For any case, if the reader believes that a particular stone is the cause of the participant's symptoms, then this will be noted. This is particularly useful in cases in which there are multiple stones. The bladder will be examined in the transverse plane at the level of the trigone to view both jets simultaneously. All participants will be scanned for 5 minutes. The number of jets from each ureteral orifice will be tabulated over time so that ureteral jet frequency, defined as number of jets per minute, can be calculated. Patients will be categorized into three groups. Group I- no ureteral jets on the symptomatic side; Group II- continuous low-level ureteral jet on the symptomatic side; Group III- ureteral jets similar to nonsymptomatic side.

In order to determine if RBUS with UJA along with clinical data confers non-inferior information compared to non-contrast CT, objective findings such as laboratory data including BMP, CBC, urine analysis and physical exam obtained as part of routine care will be retrieved from the patient's medical record and reviewed retrospectively. Clinical data and RBUS results will be de-identified/coded and the Urologist will be blinded to the CT results. Diagnosis and treatment recommendations will be determined based upon these findings and compared to those attained by CT to assess for congruence. Statistical analysis will be performed to determine non-inferiority between the studies.

Stone size and location based on CT will be recorded at the time of enrollment into the study and time to stone passage will be recorded. All study participants will be followed for stone passage. Time to stone passage will be stratified according to stone location (proximal, mid or distal ureter) and size (<2mm, 2-4mm, 5mm, 6-7mm, 9-10mm).

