7.2 Study Design

This is a single institution, prospective study to evaluate the prognostic significance of RBUS with UJA, and its utility in providing non-inferior information compared to non-contrasted CT, as well as to evaluate the spontaneous stone passage rate of ureteral stones. The study will be conducted at Washington University and will enroll approximately 100 participants over two years.

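### Secondary objective 1 promises the same or non-inferior diagnostic information to CT, but with no CT-negative participants, agreement on stone presence measures sensitivity only

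*Combined protocol and SAP*

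**What the plan says.** The aim is worded in two ways. Section 2.2 asks whether renal bladder ultrasound (RBUS) with ureteral jet assessment, combined with routine clinical data, "confers the same diagnostic information as the gold standard, non-contrast CT". Section 7.1 asks instead for non-inferior information, and Section 7.2 describes the study as evaluating "its utility in providing non-inferior information compared to non-contrasted CT". Section 5.2 announces the analysis: "Statistical analysis will be performed to determine non-inferiority between the studies".

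The comparison is made by a urologist who reviews coded history, examination, laboratory and RBUS data in order to "make an assessment and treatment recommendations". Section 7.1 adds: "The urologist will be blinded to the results of the CT". The result is compared with CT. For this objective, Section 7.3 plans diagnostic and treatment concordance and a logistic model for discordant results.

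On who enters, Section 3.1 requires "CT diagnosis of ureteral stone with a stone burden less than or equal to 10mm". Section 5.1 allows an approach when a stone is only suspected, but consent is completed later: "Following CT diagnosis of ureteral stone, study team will further discuss study participation with the patient". No study procedure may come before consent. Section 1.2 describes the population in the same way, as patients "with renal colic who have been diagnosed with a ureteral stone".

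**The concern.** A claim that one test gives the same diagnostic information as another, or no worse, concerns both patients who have the condition and patients who do not. This cohort has only the first kind. High agreement on stone presence could be reported as non-inferiority to CT while saying nothing about false positives.

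That matters because Sections 1.2 and 5.4 look toward RBUS as an alternative to imaging with ionizing radiation. In that use, the test would also be applied to people with colic and no stone.

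A second, smaller gap concerns treatment. Section 5.2 announces a non-inferiority analysis, but Section 7.3 contains none. Without a margin, the same treatment concordance could be called non-inferior or not after the data are seen.

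**Working it through.** **Inputs.**
- CT-negative participants: 0 (Sections 3.1 and 5.1).
- Planned size: about 100 (Section 7.2), with an interim analysis at 50 that may end recruitment (Section 7.3).
- Margin, confidence level and expected agreement for this objective: none stated, so the plan has no figure to reproduce. The 95% level below is my choice.

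**Step 1. The two-by-two table for stone presence.** Let TP and FN be CT-positive patients called stone and no stone, and FP and TN the same calls in CT-negative patients. Eligibility sets FP + TN = 0. Then:
- Agreement = (TP + TN) / N = TP / (TP + FN) = sensitivity.
- Specificity = TN / (TN + FP) = 0/0, not estimable.
- Positive predictive value is 100% and negative predictive value 0% by construction, wherever each is defined.
- Kappa: with observed agreement p, chance agreement is p × 1 + (1 − p) × 0 = p. So kappa = (p − p) / (1 − p) = 0 for every p below 1, and is undefined at p = 1.

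**Step 2. A reader with no information.** A reader who always says stone agrees every time. The exact (Clopper-Pearson) lower limit for n out of n is 0.025^(1/n):
- n = 100: 0.025^(1/100) = 0.964, interval 96.4% to 100%.
- n = 50: 0.025^(1/50) = 0.929, interval 92.9% to 100%.

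Measured against full agreement, this reader meets any margin wider than about 3.6 points (100 − 96.4) at n = 100, or 7.1 points (100 − 92.9) at n = 50.

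**Step 3. What the missing patients would reveal.** With CT-negative patients present, agreement = π × sensitivity + (1 − π) × specificity, where π is the CT-positive share. The documents give no π for suspected cases, so I assume 30%, 50% and 70%, with sensitivity set to 1.

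| Specificity (assumed) | π = 30% | π = 50% | π = 70% | In this trial |
|---|---|---|---|---|
| 0 (always stone) | 30% | 50% | 70% | 100% |
| 0.9 | 93% | 95% | 97% | 100% |

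For example, 0.3 × 1 + 0.7 × 0.9 = 0.93. The worthless reader and the good one are far apart in a mixed population and identical here.

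**Step 4. Treatment recommendation.** This item can differ between patients who all have a stone, so Step 1 does not apply to it. Setting the sections side by side, 5.2 promises non-inferiority, while 7.3 provides concordance and a discordance model. Neither names a margin, a decision rule or the source of the CT-based recommendation.

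**Step 5. Timing.** Section 5.2 allows RBUS up to 10 days after CT. A stone that passes in between is correctly absent on RBUS but would count as a miss against the CT. Even the sensitivity estimate may therefore be biased downward.

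**The case against.** The strongest reply is that the plan never makes stone presence the sole outcome. Section 7.1 asks for an assessment and treatment recommendations, and Section 7.3 covers diagnosis and treatment. Treatment concordance is informative among CT-positive patients. This stands, and it limits the point to the diagnostic claim. It also stands that non-inferiority of sensitivity alone, against a CT reference, can be tested in this cohort. What cannot be obtained is the wider claim.

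A reader might go further in three ways that the documents do not support.
- *That the blinding fails because enrolment reveals the stone.* The reviewed data are coded, and nothing says whether the urologist knows the eligibility rule. If so, the presence call may be biased. If not, specificity is still not estimable, so the point does not depend on this.
- *That the size bands omitting 8 mm, or the proximal/mid/distal strata, undermine this objective, or that side, size and location each lack a margin.* Those bands and strata serve secondary objective 2. Only diagnosis and treatment recommendations are named for comparison here.
- *That the study is underpowered for non-inferiority.* With no stated margin or expected concordance, any power figure would rest on invented inputs.

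**Conclusion.** The concern holds for the diagnostic part of secondary objective 1. With 0 CT-negative participants out of about 100, agreement on stone presence equals sensitivity, and perfect agreement is available to a reader who uses no ultrasound information. That result follows from the eligibility and consent rules and needs no assumption about margins or prevalence; the mixed-population figures in the working are illustrations only.

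For treatment, the defect is narrower: a non-inferiority analysis is announced in one section and not implemented in the statistical section. The primary objective and secondary objective 2 are untouched, and sensitivity and concordance remain worth estimating.

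**What to change.** In Sections 2.2, 5.2, 7.1, 7.2 and 7.3, restate secondary objective 1 as estimation among patients with a CT-confirmed ureteral stone:

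1. Sensitivity of the CT-blinded urologist's combined assessment for a ureteral stone.
2. Diagnostic and treatment concordance with CT.

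Give exact 95% intervals and the number of available pairs for each. In addition:

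- Drop *same* and *non-inferior* for diagnosis. State that specificity is not estimable and that the results do not extend to patients with colic and no stone.
- Keep *non-inferior* for treatment concordance only if a margin is fixed before any concordance data are analysed, including at the 50-patient interim. Otherwise report it descriptively.
- Name the source of the CT-based treatment recommendation. If it comes from the medical record, acknowledge that discordance then mixes differences between clinicians with differences between modalities, since Section 5.1 has patients seen by either an ED physician or a urologist.
- State whether the reviewing urologist knows that every case is CT-positive.
- Add a sensitivity analysis that excludes stones known to have passed before RBUS.

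The cost is wording in five sections and, for a record-based comparator, abstraction from records that Section 5.3 already reviews. No patients are added. A fresh CT-based recommendation by a urologist would instead add one read per participant, about 100. The downside is that the trial gives up a non-inferiority claim, but one that its design cannot support.

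### Secondary objective 1 promises a non-inferiority conclusion against CT, but section 7.3 plans only concordance and no section gives a margin, pass mark or confidence-bound rule

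*Combined protocol and SAP*

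**What the plan says.** The aim is worded in four places, all in the combined protocol and SAP:

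- Section 2.2, secondary objective 1: whether RBUS with UJA, together with routine clinical data, "confers the same diagnostic information as the gold standard, non-contrast CT".
- Section 5.2: "Statistical analysis will be performed to determine non-inferiority between the studies".
- Section 7.1, secondary outcome 1: whether the same package "confers non-inferior information compared to non-contrasted CT".
- Section 7.2: the design is meant to evaluate "its utility in providing non-inferior information compared to non-contrasted CT".

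Section 5.2 describes the comparison. A urologist blinded to CT reviews coded clinical data and the ultrasound results, and then: "Diagnosis and treatment recommendations will be determined based upon these findings and compared to those attained by CT to assess for congruence".

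Section 7.3 gives two sentences of analysis for this objective. The first is "Statistical analysis will be performed to determine diagnostic and treatment concordance between the two methods". The second is "A multivariate logistic regression model will also test patient factors that are associated with discordant results". No concordance statistic is named.

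Section 7.2 gives a size of about 100. Section 7.3 recommends an interim analysis at 50, after which recruitment may continue, be re-sized or stop. It mentions "the uncertain assumptions of the initial power analysis" without giving the inputs.

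**The concern.** A non-inferiority conclusion needs a limit fixed in advance and a rule for comparing the data with it, usually that a confidence bound must clear the limit. The plan promises the conclusion in 5.2, 7.1 and 7.2 but supplies neither. What 7.3 yields is a concordance figure and a list of factors associated with disagreement. Neither says how much disagreement with CT is tolerable.

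Followed as written, the analysis produces a number, and someone then decides whether it counts as non-inferior. That decision can go either way on the same data. The wording is also unsettled: same information, non-inferior information, congruence and concordance are different targets, and only the last reaches the analysis section.

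At stake is whether the study's stated secondary conclusion about ultrasound against CT can be supported at all.

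**Working it through.** **1. Is there a figure of the plan's own to reproduce?** No. The documents give a size of about 100 and an interim look at 50, but no alpha, power, expected concordance or margin. The figures below are therefore illustrations under assumptions.

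**2. Is the rule stated elsewhere?** I compared 2.2, 5.2, 7.1, 7.2 and 7.3. Three state non-inferiority, one states sameness, and 7.3 states concordance. None gives a limit or bound. The text for this objective in 7.3 is continuous, with no sign of redaction.

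**3. Assumptions for the illustration.** One concordance proportion, x concordant out of n, all patients evaluable. Non-inferiority is declared if the lower bound of the exact (Clopper-Pearson) two-sided 95% interval exceeds a pass mark. The lower bound is the 2.5% quantile of Beta(x, n − x + 1). The upper bound is the 97.5% quantile of Beta(x + 1, n − x).

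**4. One result, two verdicts.** For x = 90, n = 100:
- lower bound, 2.5% quantile of Beta(90, 11) = 0.824
- upper bound, 97.5% quantile of Beta(91, 10) = 0.951

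The lower bound of 82.4% exceeds 80%, so the result passes that mark. It is below 85%, so it fails that one.

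**5. How far the pass mark drives the verdict.** The smallest passing x at n = 100 comes from step 3. The last column is the binomial probability of reaching it, P(X ≥ x), if true concordance is 90%.

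| Pass mark | Smallest passing x of 100 | Chance of passing at true 90% |
|---|---|---|
| 75% | 84 | 97.9% |
| 80% | 89 | 70.3% |
| 85% | 93 | 20.6% |

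**6. Alpha and interval method matter too.** For 88 of 100 and an 80% mark:
- exact lower bound, one-sided 0.025: 79.98%, fails
- exact lower bound, one-sided 0.05: 81.3%, passes
- Wilson lower bound, one-sided 0.025: 80.2%, passes

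If recruitment stopped at 50, 45 of 50 has exact lower bounds of 78.2% (one-sided 0.025) and 80.1% (one-sided 0.05), which again split at 80%.

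**The case against.** The best defence is that non-inferior is used loosely. Section 2.2 speaks of sameness, 5.2 of congruence and 7.3 of concordance, so the intention may simply be to describe agreement. This is also a secondary objective in a single-institution study of about 100, and the blinded assessment is a retrospective review, so the primary result does not depend on it. Much of this stands, and it limits the weight of the point. It does not remove it: 5.2 says outright that the statistics will determine non-inferiority, and 7.2 makes it a design aim. If only agreement is meant, the text should say so.

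A reader might infer more than the documents support:

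- **That the plan will use a test that points the wrong way**, such as reading a non-significant McNemar test, or agreement better than chance, as non-inferiority. Section 7.3 names no McNemar test, kappa or chi-square test for this objective; its chi-square test belongs to the primary objective. The risk can be illustrated for treatment recommendation only: with 15% against 5% discordant (assumed), an exact McNemar test at two-sided 0.05 is non-significant about 46% of the time at n = 100 and 76% at n = 50.
- **That such figures carry over to stone diagnosis.** Section 3.1 requires a CT diagnosis of ureteral stone, so no participant is CT-negative. A chi-square test against chance cannot be computed for stone presence. A 10-point shortfall there is 10% against 0%. With all disagreement in one direction the exact two-sided p-value is 2 × 0.5^d for d discordant patients, so significance needs d ≥ 6. The non-significant probability is P(d ≤ 5): about 6% at n = 100 and 62% at n = 50.
- **That 100 patients are known to be too few, or were not sized for this objective.** Power depends on agreement rates the documents do not give, and the inputs of the initial power analysis are not shown. One can say only that no link between the size and this objective is shown.
- **That the result would lead to CT being replaced.** Section 5.4 says only that the findings may help define the role of ultrasound.

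**Conclusion.** The point holds. The plan states a non-inferiority conclusion in 5.2, 7.1 and 7.2 that the analysis in 7.3 cannot deliver, because no limit or decision rule exists and concordance alone does not supply one. This is a gap between claim and method, not just a missing detail.

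The illustration shows that the choice left open can decide the answer: at true concordance of 90%, moving the pass mark from 75% to 85% takes the chance of a non-inferior verdict from about 98% to 21%. It rests on assumed concordance and pass marks, a single proportion, an exact 95% interval and 100 evaluable patients. The absence of a rule rests on the text alone.

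It should be corrected, as a secondary-objective issue.

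**What to change.** Before any concordance data are seen, make 2.2, 5.2, 7.1, 7.2 and 7.3 agree in one of two ways.

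**Default, since no margin is given.** Remove the non-inferiority and same-information wording. State the objective as estimating how far the CT-blinded assessment agrees with CT, separately for diagnosis and for treatment recommendation, each with an exact 95% confidence interval and no non-inferiority conclusion.

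**If the claim is kept.** In 7.3:
- name the agreement measure;
- say whether diagnosis, treatment recommendation or both must pass;
- fix a minimum acceptable value with a clinical justification;
- declare non-inferiority only if the lower bound of the two-sided 95% interval exceeds that value;
- state that neither a non-significant difference nor agreement above chance will be read as non-inferiority.

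No power statement should be added as fact unless its assumed agreement rates are given with it.

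The cost is wording in five sections, with no extra patients, scans or readers. The downside is a weaker secondary claim under the default, or a claim that may fail if it is kept.
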